The purpose of this investigator-initiated prospective observational cohort study is to establish the new UCLA Perinatal Biospecimen Repository (Perinatal Repository) for collection, storage, and distribution the human data and biospecimens of the participants with perinatal pathology. The secure and shared high-quality resource of clinical data and biological specimens (Repository Materials), across pregnancy pathology related to research protocols at the [name]'s Lab will be created. Core variables of interest include clinical characteristics and relevant biological samples. Intention to collect perinatal data is aiding the efficiency and effectiveness of de-identified biorepository for pregnancy-at-risk outcome research.

The primary aims of the project are:

- To design the Case Report Forms (CRFs) for the clinical and biospecimen data.
- To create and update the project-specific policies, agreements, and Standard Operating Procedures (SOPs).
- To develop the data management system to assure personal health information de-identification, data integrity, participants welfare, and protocol compliance.
- To develop and implement a quality management system for the Repository.
- To collect and record in the Repository protocol-related clinical information.
- To organize consistent system to bank high-quality biospecimens while protecting participant-donor safety and privacy.
- To establish the policies and procedures for Repository Materials dissemination and research collaboration.
- To analyze the scientific results of the Repository creation.

The secondary aim of the study is to provide a mechanism to store and share for the research purposes the de-identified biospecimen and information about participants at risk for adverse pregnancy outcomes.

Inclusion criteria: 1. Pregnant and postpartum birthing persons aged 18 and over with perinatal pathology; 2. Pregnant and postpartum birthing persons; 3. Non-pregnant birthing persons (volunteers).

Exclusion criteria: Pregnant and postpartum birthing person unwilling to give written informed consent to participate in the study.

Duration of the project – 5 years. Approximate number of participants – 1000. The number of visits – from one to 6. Duration of the subject's participation in the study - from 1 day to 10 months. Follow-up period: from enrollment to postpartum visit. Core variables of interest comprise of the birthing person's/ fetus'/ neonate's clinical characteristics and relevant biological samples: maternal blood, cord blood, plasma, serum, urine, breastmilk, placenta, umbilical cord, amniotic fluid, product of conception (POC), and cell lines. Collection and retaining of the biospecimens will be performed by study team across perinatal pathology cases at the UCLA Health Medical Centers for up to 15 years. Study medical procedures (blood drawing, assessment, physical examinations, medical record, etc.) will be conducted by appropriately licensed/ credentialed personnel working within the scope of their licenses and credentials. Dataset entry and specimens processing will be performed by the [name]'s Lab personnel at the University of California, Los Angeles.

Key words: Biospecimen, Perinatal, Pregnancy, Repository, Obstetrics

1 BACKGROUND INFORMATION AND RATIONALE

1.1 Introduction

According to the US Centers for Disease Control and Prevention, complications of pregnancy involve the mother's health, the neonate's / fetus' health, or both. Some birthing persons can have perinatal disorders that arise during or after pregnancy. Other patients have health problems before they become pregnant that could lead to pregnancy complications. It is very important to know the risk factors of perinatal disorders to prevent non-favorable pregnancy outcomes. For pregnant and postpartum persons and also for their neonates/ fetuses implementation the results of scientific study into clinical care mean to decrease the risk of pregnancy complications.

At the present time, [name] is conducting and overseeing the series of scientific projects in the field of perinatal pathology, including the following:

- PRIORITY (Pregnancy CoRonavIrus Outcomes RegIsTrY). It is the nationwide study of pregnant or recently pregnant persons who are either under investigation for Coronavirus infection (COVID-19) or have been confirmed to have COVID-19. This research is being performed to help patients and healthcare providers better understand how COVID-19 impacts pregnant persons and the newborns.
- Prenatal Vascular Phenotype in Congenital Heart Disease (CHD). This project targets the mechanisms underlying the single heart ventricle vascular phenotype by linking molecular data and environmental clues. Single ventricle accounts for 25% of infant CHD deaths; only 50-70% babies with this disease survive beyond 5 years. Research results may improve treatment that arises from loss of vascular integrity.
- Endothelial Cells: Conduits of Translational Medicine. Evaluation of the umbilical cord vessels provides data to identify the biomarkers responsible for the underlying etiologies of preeclampsia, growth restriction, and other pregnancy-related disorders.
- The Umbilical Cord as a Model System. The project identifies a patient population with an unmet clinical need because of an underlying chronic dysfunction of hemodynamics related to endothelial cell dysfunction. The study analyses downstream complications and interventions that can improve quality of life in these patients with lifelong sequel related to an abnormal endothelial cell and vascular phenotype. The project focuses on altered flow acting as a modifier in development and contributing to CHD. Flow is a well-defined mechanism and provides a platform to study physical forces that alter hemodynamics and of critical importance of gene expression in prenatally diagnosed CHD with postnatal sequel related to the vascular phenotype.

Creation and maintenance of Perinatal Repository provides the [name]'s Lab with the possibility to pool perinatal clinical data and biospecimens into a single database that could be accessed by clinical investigators inside and outside the UCLA research team.

The secure and shared research data storage and high-quality resource of clinical data and biological specimens (Repository Materials), across pregnancy pathology related to research protocols at the [name] will be created. Core variables of interest include clinical characteristics and relevant biological samples. Collection and retaining of the

biospecimen will be performed by study team across perinatal pathology protocols at the [name]'s Lab.

The core data variables are selected to match those agreed upon by the [name]'s Lab team members. Intention to collect perinatal data is aiding the efficiency and effectiveness of de-identified biorepository for pregnancy at risk outcome research.

1.2 Compliance Statement

This study will be conducted in full accordance with Good Clinical Practice (GCP) and as required by the following regulations:

- University of California, Los Angeles (UCLA), Office of Research Administration Research Policies and Procedures;
- UCLA Human Research Protection Program;
- UCLA IRB Guidance and Procedures;
- United States Code of Federal Regulations (CFR): 21 CFR Parts 11 (Electronic Records and Electronic Signatures), 50 (Protection of Human Subjects), 54 (Financial Disclosure by Clinical Investigators), 56 (Institutional Review Boards), and 45 CFR Part 46 (Protection of Human Subjects);
- Health Insurance Portability and Accountability Act (HIPAA): Privacy Rule and Security Rule;
- U.S. Department of Health and Human Services, Food and Drug Administration (FDA) Guidance Documents, as applicable;
- International Conference on Harmonization (ICH) guidelines, but not limited to Good Clinical Practice (ICH E6), Clinical Trials in the Pediatric Population (ICH E11), and Genomic Sampling (ICH E18);
- the Belmont Report; the Declaration of Helsinki;
- National Institutes of Health (NIH) Office of Extramural Research, Research Involving Human Subjects, as applicable;
- International Society for Biological and Environmental Repositories (ISBER) best practices;
- Applicable Federal, State, Local Regulations and Guidance.

Non-compliance issue, if any episode arises, will be timely documented. The PI will conduct the study in due course with this clinical protocol, will obtain consent and assent (unless a waiver is granted), and will report unexpected issues in conformity with the UCLA IRB policies and procedures and applicable federal, state, and local requirements. Obtaining, recording, reporting and transmission of research data will comply with the regulations mentioned above to protect the privacy, health, and welfare of the research participants during and after the study and to ensure the integrity of the data collected.

2 STUDY OBJECTIVES

The purpose of this investigator-initiated prospective observational cohort study is to establish the new UCLA Perinatal Biospecimen Repository for collection, storage and distribution the human data and biospecimens of the participants with perinatal pathology.

As a result of the clinical protocol implementation, the secure and shared research data storage and high-quality resource of clinical data and biological specimens, across perinatal pathology related to research protocols at the [name]'s Lab will be created.

2.1 Primary Aims

The primary aims of the project are:

1. To design the case report forms (CRFs) for the clinical and biospecimen data.
2. To create and update the project-specific policies, agreements, and Standard Operating Procedures (SOPs).
3. To develop the data management system to assure personal health information de-identification, data integrity, participants welfare, and protocol compliance.
4. To develop and implement a quality management system for the Perinatal Repository.
5. To collect and record in the Repository protocol-related clinical information.
6. To organize consistent system to bank high-quality biospecimens while protecting participant-donor safety and privacy.
7. To establish the policies and procedures for Repository Materials dissemination and research collaboration.
8. To analyze the scientific results of the Repository creation.

2.2 Secondary Aim

The secondary aim of the study is to provide a mechanism to store and share the de-identified biospecimen and information about participants at risk for adverse pregnancy outcomes for the research purposes.

2.3 Hypothesis

There is no hypothesis for this patient repository study.

3 INVESTIGATIONAL PLAN

3.1 Study Design

This is a Phase 0, investigator-initiated, prospective, observational study design: Patient Registry.

Observational Model: Cohort.

Time Perspective: Prospective.

Follow-Up Duration: From enrollment to postpartum visit.

The study is designed to create Repository of biospecimen and clinical data that may allow earlier evaluation of the patient's risk of developing adverse pregnancy outcomes. Further in this protocol, the term "Material/ Materials" is used to refer to human data and/ or biospecimens collected from the research participants. This study will be conducted in UCLA Health collecting data of the inpatients and outpatients with perinatal pathology and birthing persons (volunteers). All study participants will continue to be managed by their personal physicians / pediatrician. Participants will receive the treatment recommended by their doctors; the study will not alter the treatment pathway and pregnancy management of the patients. This study does not restrict or introduce any therapeutic or surgery interventions, including medications.

Along with biological specimens, this Register aims to collect and record the current treatment and outcomes during and after the pregnancy of participants diagnosed with perinatal pathology. Participants' information and biospecimen will be obtained as described below in Study Procedures. The Repository will contain the new research database of perinatal pathology.

3.1.2 Institutional Review Board Information

Protocol of the study will be sent to the local UCLA IRB that is registered by the OHRP/ FDA [<https://ohrp.cit.nih.gov/search/IrbDtl.aspx>].

Parent Institution/Organization: IORG0000105 - University of California Los Angeles.

Located at: Los Angeles, California, US.

Expires: 12/10/2021.

IRB00000172 - University of California Los Angeles - MIRB1 General Biomedical IRB #1 - General Biomedical - MIRB1-Biomedical

3.1.3 Overview of the Data Collection

After enrollment of the participant in the study, PI/ designee study personnel (according to Study Delegation Log) will conduct chart review, i.e., manually review patient chart in CareConnect. To contribute to the Perinatal Registry database, clinical information of inpatient and outpatient population will be collected. Patient encounters are related to Ronald Reagan Hospital and Santa Monica Hospital.

Biospecimens will be collected prospectively to the Perinatal Repository. Clinical data will be linked to the biospecimens. Dataset entry and specimens processing will be performed at the [name]'s Lab.

3.2 Study Duration, Enrollment and Number of Sites

3.2.1 Duration of the Study

Duration of the project – 5 years.

Duration of participation in the study - from 1 day to 10 months.

Duration of follow-up period – from enrollment to postpartum visit.

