4.1.2. Schedule of Events

Recruitment of pregnant birthing persons and volunteers will happen consecutively at the UCLA Health facilities. Table 1 outlines the events and biospecimen collection schedule for the study.

Table 1. Schedule of Events

Procedures/ Assessments	Enrolment/ Baseline Visit	The Stages of Pregnancy				Postpartum Visit ^d
		1 st Trimester (from conception to 12 weeks)	2 nd Trimester (from week 13 to week 27)	3 rd Trimester: (from week 28 until birth)	Delivery/ End of Pregnancy	
Eligibility Criteria	X					
Informed	X ^a					

Consent						
Medical History ^c	X	X ^b				
Pregnancy Status	X	X ^b				
Pregnancy Outcomes					X ^b	X ^b
AE	X	X ^b				
Neonatal/ Fetal Status	X	X ^b				
Neonatal/ Fetal Outcomes					X ^b	X ^b
Biospecimens Banking ^e:						
Blood ^f	X	X ^b				
UC Blood					X ^b	
Urine	X ^b	X ^b	X ^b	X	X ^b	X ^b
Tissue: Placenta					X ^b	
Tissue: UC					X ^b	
Other Tissue: POC ^g					X ^b	
Amniotic fluid					X	
Breastmilk						X ^b

Footnotes for Schedule of Events:

X: Required activities.

^a : Informed Consent process should take place prior to undergoing any Protocol-specific procedures.

^b : Optional, based on the PI decision.

^c : Medical History includes, but not limited to: demographics, physical examination, concomitant medications, ECG, laboratory assessment. Laboratory assessment includes, but is not limited to hematology, blood chemistry, coagulation, endocrine function, urinalysis, serum/ urine pregnancy test, TORCH infections: toxoplasmosis, rubella virus, cytomegalovirus, and HIV. Procedures and assessments will be performed according to the routine standard at the UCLA Health, and are documented as available (with the exception of Informed Consent).

^d : Postpartum Visit should take place within 6 months of delivery/ end of pregnancy.

^e : For biospecimens banking, trained research team personnel will collect the biospecimens per standard operating procedures.

^f: The study protocol provides for the collection of blood samples as a procedure combined with routine blood sampling for clinical laboratory testing. For research purposes, it is intended to collect additional amount of the venous blood – up to 20 mL per procedure. The blood will not be drawn for research more often than twice in a single week. Blood drawing will be performed as follow: Red Top Tube (Serology tube) – 10 mL and Lavender Top Tube (EDTA tube) – 10 mL. Blood samples will be collected for whole blood, plasma, and serum banking.

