^g : Other tissue: In case of a miscarriage, abortion, or stillbirth, the participant will be asked to donate POC tissue for Repository collection.

Participation in the Repository Protocol can be offered by the PI/ designee for the outpatients and inpatients. Eligibility criteria will be checked during baseline visit. Informed consent form should be signed at enrolment, following which baseline medical history will be collected. Medical history includes, but not limited to demographics, physical examination, concomitant medications, ECG, laboratory assessment. Information about pregnancy and fetal status will be recorded. Laboratory assessment includes, but is not limited to hematology, blood chemistry, coagulation, endocrine function, urinalysis, serum/ urine pregnancy test, TORCH infections: toxoplasmosis, rubella virus, cytomegalovirus, and HIV. Procedures and assessments will be performed according to the routine standard at the UCLA Health, and are documented as available (with the exception of Informed Consent).

Enrolment/ Baseline Visit: After consenting, the birthing person will be asked to donate blood (maternal blood) or/ and urine specimen to the Repository. Trained research team personnel will collect the biospecimens per standard operating procedures. The study protocol provides for the collection of blood samples as a procedure combined with routine blood sampling for clinical laboratory testing.

For research purposes, it is intended to collect additional amount of the venous maternal blood – up to 20 mL per procedure. The blood will not be drawn for research more often than twice in a single week. Blood drawing will be performed as follow: Red Top Tube (Serology tube) – 10 mL and Lavender Top Tube (EDTA tube) – 10 mL. Blood samples will be collected for whole blood, plasma, and serum banking.

Collection of the cord blood after delivery will be performed once as the same order. The research Protocol does not involve collecting any specimens of the vital neonates, such as venous blood or urine.

All biological sampling for the Repository (blood, urine, breastmilk, placenta, umbilical cord, i.e.) will follow the [name]'s Lab standard operating procedures, UCLA, local and federal guidance documents on the proper handling and processing of potentially infectious biospecimens.

After participant enrollment, the PI will monitor and record, if any, the AEs, and informs the UCLA IRB according to the established policy and regulations.

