Follow-up Visits: For pregnant birthing persons, biospecimens donation during follow-up visits is optional, based on the PI decision. Repository Material will be collected by research team during follow-up research visits (each once per pregnancy trimester):

- 1st Trimester Visit (from conception to 12 weeks): medical history, pregnancy and fetus status, AE, biobank specimens: blood and urine.
- 2nd Trimester Visit (from week 13 to week 27): medical history, pregnancy and fetus status, AE, biobank specimens: blood and urine.
- 3rd Trimester Visit: (from week 28 until birth): medical history, pregnancy and fetus status, biobank specimens: blood and urine.

Delivery/ End of Pregnancy Visit: Medical history, pregnancy status, pregnancy outcome, neonatal/ fetus status, neonatal/ fetus outcome, AE, biobank specimens: maternal blood, cord blood (UC blood), maternal urine, placenta, umbilical cord, amniotic fluid.

Umbilical cord and placenta are temporary fetus organs. For the Repository collection, placenta, umbilical cord, and therefore, cord blood, will be obtained for the Repository purposes after childbirth.

In case of a miscarriage, abortion, or stillbirth, the participant will be asked to donate POC tissue to the Repository.

Postpartum Visit: Medical history, pregnancy outcome, neonatal status, neonatal outcome, AE, biobank specimens: maternal blood, maternal urine, breastmilk.

All biological sampling for the Repository (blood, urine, breastmilk, placenta, umbilical cord, i.e.) will follow [name]'s Lab standard operating procedures, UCLA, local and federal guidance documents on the proper handling and processing of potentially infectious biospecimens.

For non-pregnant volunteers, participation in the project is limited to the one-time biospecimens donation and granting access to their medical records.

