5.4.2 Standard of Care

Screening and enrollment of study participants will be organized on the labor and delivery units at both Ronald Reagan Medical Center and Santa Monica Hospital. High-professional physicians, nurses, midwives, and staff of the Department of Obstetrics and Gynecology represent the nationally and internationally recognized leaders in the delivery of women's medical care. The provision of patient care is carried out in accordance with the strict standards of medical care implementation at the David Geffen School of Medicine at UCLA.

Whatever the birthing person does consent / or does not consent the participation in the study, it will not change the person's labor management.

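### Is the stated 10-month maximum participation too short for the protocol's own visit windows?

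*Protocol*

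**What the plan says.** Section 3.2.1 of the Protocol states "Duration of participation in the study - from 1 day to 10 months" and, on the next line, "Duration of follow-up period – from enrollment to postpartum visit". The Abstract repeats the range ("Duration of the subject's participation in the study - from 1 day to 10 months") and adds "The number of visits – from one to 6". Table 1 in section 4.1.2 accounts for the six visits: baseline, one in each trimester, delivery or end of pregnancy, and postpartum. The first-trimester window runs from conception to 12 weeks. Footnote d sets the last window: "Postpartum Visit should take place within 6 months of delivery/ end of pregnancy".

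On when people join, section 4.1.2 says "Participation in the Repository Protocol can be offered by the PI/ designee for the outpatients and inpatients", so antenatal enrollment in clinic is allowed. Section 5.4.2, on the other hand, says "Screening and enrollment of study participants will be organized on the labor and delivery units".

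The Combined protocol and SAP has the same duration range and the same footnote d, so this is not a difference between versions. Neither document explains where the 10 months comes from.

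**The concern.** Ten months is given as the top of a range, and 6 months as the top of the postpartum window. Subtracting one from the other leaves 4 months for everything between enrollment and delivery. A schedule with a first-trimester visit plainly expects some people to be enrolled for longer than that before they deliver. A postpartum visit that is on time under footnote d can therefore fall after the stated participation has ended.

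If the 10 months worked as a limit, three things would be at stake: whether late postpartum blood, urine, breastmilk and outcome data were collected within the approved duration, whether the ethics board had been told the right length of involvement, and when a participant counts as lost to follow-up.

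**Working it through.** **Inputs.** From the documents: stated maximum 10 months (3.2.1, Abstract); follow-up from enrollment to the postpartum visit (3.2.1); postpartum visit up to 6 months after delivery (Table 1, footnote d); first-trimester visit up to week 12 (4.1.2). Assumed, because the documents do not give it: delivery at 40 weeks, range 37 to 42. Conversion: 365.25/12/7 = 4.348 weeks per month, so 6 months = 26.09 weeks and 10 months = 43.48 weeks.

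**Can the 10 months be reproduced?** Not from the full windows. A value close to it appears if a nearly complete pregnancy is paired with an early postpartum visit: enrollment at week 2, delivery at 40 and a visit 6 weeks later give (40 − 2 + 6)/4.348 = 10.1 months. That pairing is only an illustration; the documents do not state it.

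**Longest duration the windows allow** = (delivery week − enrollment week)/4.348 + 6 months.

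| Enrolled at week | Delivery 37 | Delivery 40 | Delivery 42 |
|---|---|---|---|
| 2 (about conception) | 14.05 | 14.74 | 15.20 |
| 8 | 12.67 | 13.36 | 13.82 |
| 12 | 11.75 | 12.44 | 12.90 |
| 24 | 8.99 | 9.68 | 10.14 |

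Week 12 is the latest enrollment that still falls in the first-trimester window, so 12.4 months is an example and not the longest path. Counting weeks from conception, with birth at an assumed 38, the week-12 case gives 26/4.348 + 6 = 12.0 months, which leaves the conclusion unchanged.

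**Who could exceed 10 months.** The full window fits only if enrollment is at or after delivery week − (43.48 − 26.09) = delivery week − 17.39. That is about week 22.6 for delivery at 40 weeks (19.6 at 37, 24.6 at 42). Anyone enrolled at delivery has at most 6 months.

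**Can both statements be met?** Weeks left for the postpartum visit under 10 months = 43.48 − (delivery week − enrollment week). For delivery at 40 weeks:

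- enrolled at week 12: 43.48 − 28 = 15.5 weeks
- enrolled at week 8: 43.48 − 32 = 11.5 weeks
- enrolled at week 2: 43.48 − 38 = 5.5 weeks (3.5 if delivery is at 42)

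All are positive. In every case shown, some postpartum visit date satisfies both the footnote and the range.

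**Does anything use the 10 months?** Follow-up ends at an event, the postpartum visit. Loss to follow-up in section 4.1.7 depends on the participant's planned end-of-study visit, not on a count of months. The timing of specimens is set by Table 1 and the visit descriptions in 4.1.2. Section 2.3 states that there is no hypothesis, and section 5.3.3 that no SAP is written. No rule, visit or calculation refers to month 10.

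**The case for a change.** The strongest case for acting is that both figures are maxima and the two maxima disagree. Saying that 6 months is only an upper bound does not remove this, because 10 months is also an upper bound and no section shortens the postpartum window for people enrolled early. Enrollment on the delivery units does not settle it either: outpatients may be offered participation, section 5.6.2 allows recruitment at perinatal visits, and the trimester columns would be pointless if everyone joined at delivery. Follow-up being optional does not help, since an optional visit is still a permitted one. The Abstract marks the participant number as approximate but does not mark the duration that way. Correcting it would take one figure or one footnote.

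The textual part of this stands: the range is shorter than the schedule allows, and nothing reconciles the two. The consequence does not stand. The 10 months is written as a description of how long participation lasts, with no instruction attached to it, and staff working from Table 1 and footnote d would collect the same material at the same times whatever the summary figure said. A participant-facing conflict cannot be shown either, because the consent text is not among the documents reviewed.

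**Conclusion.** The observation is correct, but it does not warrant a change to the plan. With the full postpartum window, a participant enrolled at week 12 could be followed for about 12.4 months (11.75 to 12.9 for delivery at 37 to 42 weeks), roughly 2.4 months beyond the stated maximum, and earlier enrollees for longer. This rests on the assumed pregnancy length and on the visit being held at the very end of its window. The share of participants enrolled before about week 22.6 is not given.

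The figure is a loose summary, close to a clerical slip. It can be met together with footnote d, it triggers no action, and the event-based end of follow-up already tells staff when participation ends. With no hypothesis, power calculation or planned analysis, aligning the numbers would change no result, bias, precision or safety measure. The repository obtained by following the schedule as written would be the same.
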